## 13 ADVERSE EVENTS

### 13.1 Definition

An adverse event (AE) is defined as any untoward medical occurrence in a subject or clinical investigation subject administered a pharmaceutical or medical device product that does not necessarily have a causal relationship with this treatment. Adverse events include the following: all suspected adverse device or procedure reactions, occurrence of apparently unrelated illnesses

(i.e., symptoms or diseases that were not present at study entry), worsening of a pre-existing illness (i.e., concurrent symptoms or diseases), injuries or accidents, and abnormalities in physiological or laboratory testing or physical examination findings that require clinical intervention or further investigation (beyond ordering a repeat confirmatory test). Throughout the study, subjects will be monitored for signs and symptoms of adverse events.

All adverse events reported during the study period will be recorded in detail in the subject's medical file and CRF.

### **13.2 Recording of Adverse Events**

Subjects will be instructed by the PI to immediately report the occurrence of any adverse event. Each subject should be questioned at all visits whether any side effects or adverse events have occurred. All spontaneously volunteered, inquired, and observed adverse experiences will be recorded in detail.

### **13.3 Serious Adverse Events and Unanticipated Adverse Device Effects**

#### **13.3.1 Definition**

Serious Adverse Events (SAEs) are defined as undesirable events experienced by a subject that suggest a significant hazard, contraindication, side effect, or precaution, whether or not considered to be device-related by the Investigator. An AE is defined as being serious if:

1. It is fatal or life threatening (life threatening means that in the opinion of the Investigator, the subject was at immediate risk of death from the adverse reaction)
2. It is permanently or temporarily disabling
3. It requires inpatient or prolonged hospitalization
4. Is a congenital anomaly/birth defect

An unanticipated adverse device effect is defined as any serious adverse effect on health or safety, any life threatening problem, or death that was not previously identified in nature, severity, or degree of incidence in the investigational plan or application (including a supplementary plan or application), or any other unanticipated serious problem associated with a device that relate to the rights, safety, or welfare of subjects.

#### **13.3.2 Serious Adverse Events Recording and Reporting**

Any serious and/or unexpected adverse event that occurred while on study or one month after completion of study must be reported to DeNova Research via telephone. The Serious Adverse Event Report Form must be completed and faxed to DeNova Research and IRB within 24 hours of notification.

In addition, the local IRB or EC must be notified of all adverse events that are serious and/or unexpected.

All adverse events, including serious and unexpected events, must be recorded by the Investigator on the standard Adverse Event Report form. This form will be included in the CRF. All Adverse Event Reports describing adverse events other than serious or unexpected adverse events will be inserted into the CRF. In addition, any serious and treatment-related unexpected adverse events must be reported to the local IRB within 5 business days of the event.

Subjects who have had a serious adverse event must be followed clinically until all parameters, including laboratory values, have either returned to normal or are otherwise explained. If death was the outcome of the event on the initial Adverse Event Report, a Follow-up/Final Report, including an autopsy report, when performed, must be completed.

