## 9.2 Visit 2: Treatment

Visit 2 will take place no later than 14 days after the screening assessments. If the period between the screening assessments and the treatment is greater than 14 days, the in-clinic urine pregnancy test will be repeated for females of childbearing potential. The following procedures will be performed:

1. Subject's medical history and concomitant medications are reviewed for changes since Visit 1, Screening Assessments.
2. PI rates the subject on the OCSS and POLSS at rest.
3. The injection area is wiped with a Benzalkonium Chloride towelette.
4. A topical anesthetic containing 30% lidocaine is applied to the injection areas. Alternatively, subject may choose to receive a nerve block, infraorbital/mental with 3% mepivacaine, to numb the treatment area.
5. Subject is injected with Restylane® Silk with a volume sufficient to deliver satisfactory cosmetic results per treating investigator's discretion but not to exceed a total of 4 ml (4 syringes).
6. The volume injected is recorded.
7. The subject is monitored for any Adverse Events (AEs)

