## 9.3 Visit 3: OCR Evaluation

The following procedures will be performed 14 ± 3 days after Visit 2, Treatment:

1. PI assesses the subject for achieving the OCR.
2. At PI's discretion, subject may receive a touch-up treatment in order to achieve OCR (not to exceed a total dose of 4 ml of Restylane® Silk).
3. A report of any AEs and changes in concomitant medications is obtained from the subject.

Subjects who require a touch-up injection will be instructed to return for the forth and final visit in 14 ± 3 days. For those who have achieved OCR, and hence do not require a touch-up injection, the following procedures will be performed:

1. Subject completes the SHS questionnaire.

2. Subject completes the HM questionnaire.
3. Subject completes a self-reported GAIS (S-GAIS).
4. PI completes the GAIS form (PI-GAIS).
5. PI rates the subject on the OCSS and POLSS at rest.
6. Subject undergoes standardized digital photography and video of full face in accordance with the site's SOP (described in Appendix I);

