#### **9.4 Visit 4: 14-Day Post-OCR**

Visit 4 will take place 14 ± 3 days after Visit 3, OCR Evaluation only for subjects who required a touch-up injection in Visit 3 in order to achieve OCR.

The following procedures will be performed:

1. Subject completes the SHS questionnaire.
2. Subject completes the HM questionnaire.
3. Subject completes a self-reported GAIS (S-GAIS).
4. PI completes the GAIS form (PI-GAIS).
5. PI rates the subject on the OCSS and POLSS at rest.
6. Subject undergoes standardized digital photography and video of full face in accordance with the site's SOP (described in Appendix I);
7. A report of occurrence of any AEs and changes in concomitant medications is obtained from the subject.

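### Serious or unexpected events stay reportable for a month after the study, but no adverse event query is scheduled in that month; one recorded contact per subject would be a cheap improvement

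*Combined protocol and SAP*

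**What the plan says.** Section 13.3.2 sets the reporting window: "Any serious and/or unexpected adverse event that occurred while on study or one month after completion of study must be reported".

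Section 13.2 describes how events come to light. Active questioning belongs to visits: "Each subject should be questioned at all visits whether any side effects or adverse events have occurred". Alongside it are two routes not limited to visits: "Subjects will be instructed by the PI to immediately report the occurrence of any adverse event", and "All spontaneously volunteered, inquired, and observed adverse experiences will be recorded in detail".

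Section 9 and Appendix A give the schedule:

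- Visit 2 (Section 9.2) lists adverse event monitoring on the day of injection, after the injection step.
- Visit 3 (Section 9.3) is timed as follows: "The following procedures will be performed 14 ± 3 days after Visit 2, Treatment". At that visit, "A report of any AEs and changes in concomitant medications is obtained from the subject". In the list of procedures this comes after any touch-up.
- Visit 4 (Section 9.4) is not for everyone: "Visit 4 will take place 14 ± 3 days after Visit 3, OCR Evaluation only for subjects who required a touch-up injection". It also includes an adverse event report.
- In Appendix A the column after Visit 4 contains only the FIQ, which is photograph rating without subject contact (Section 9.5).

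The synopsis ends subject follow-up 14 days after the treatment that produced the optimal result.

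**The concern.** The protocol chose to make events in an additional month reportable, yet plans no occasion in that month on which anyone asks. During the visits it uses questioning and spontaneous reporting together; afterwards only the spontaneous route remains.

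The duty covers unexpected events as well as serious ones, so it includes unexpected events that are not serious. In my judgement, a subject who has finished her visits may not recognise such an event as worth a call. The documents neither support nor contradict that.

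At stake is the completeness of the safety record in a window the protocol set for itself. Section 12.3 lists no safety endpoint, so no primary or secondary analysis depends on it.

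**Working it through.** The plan gives no figure for adverse event capture, so there is none to reproduce. The check is a comparison of the schedule with the window, followed by day counts.

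**1. Scheduled queries against the reportable period**

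| Subject | After last injection, same day | Later scheduled query | In the added month |
|---|---|---|---|
| No touch-up | Visit 2 monitoring | Visit 3, 11–17 days later | none |
| Touch-up | Visit 3 report, listed after the touch-up | Visit 4, 11–17 days later | none |

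The 11–17 days come from the 14 ± 3 day windows in Sections 9.3 and 9.4.

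**2. Share of time without a scheduled query**

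Inputs: F = days from first injection to last visit (Sections 6, 9.3, 9.4 and Appendix A); M = length of the added month. Assumption: M = 30 days, counted from the subject's last visit. Formula: share = M / (M + F).

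| Case | F (days) | Share |
|---|---|---|
| No touch-up, nominal | 14 | 30/44 = 68.2% |
| No touch-up, limits | 17; 11 | 30/47 = 63.8%; 30/41 = 73.2% |
| Touch-up, nominal | 28 | 30/58 = 51.7% |
| Touch-up, limits in Section 6 and Appendix A | 31; 25 | 30/61 = 49.2%; 30/55 = 54.5% |
| Touch-up, both Section 9 windows added | 34; 22 | 30/64 = 46.9%; 30/52 = 57.7% |

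With a month of 28 to 31 days, the range without touch-up is 28/45 = 62.2% to 31/42 = 73.8%. With touch-up it is 28/62 = 45.2% to 31/53 = 58.5%.

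**3. Effect of one extra contact**

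Scheduled queries in the added month rise from 0 to 1 per subject. Queries on a later day than the last injection rise from 1 to 2. Total: 20 subjects × 1 = 20 contacts.

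**4. Can the gain be estimated?**

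Only with assumed inputs. Let r be the proportion of subjects with a reportable event in the month and c the probability that it reaches the site. The chance of recording at least one event among 20 subjects is 1 − (1 − rc)^20. None of the values below is in the documents; 95% capture with a contact is also assumed.

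| r | c = 30% | c = 50% | c = 80% | c = 95% (with contact) |
|---|---|---|---|---|
| 1% | 5.8% | 9.5% | 14.8% | 17.4% |
| 5% | 26.1% | 39.7% | 55.8% | 62.2% |
| 10% | 45.6% | 64.2% | 81.1% | 86.4% |

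At r = 5%, for example, the gain is 36 points if passive capture is 30% and 6 points if it is 80%. The assumption decides the answer.

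**The case against.** The strongest reply is that nothing is broken. Section 13.3.2 is a duty to report what becomes known, with a form due within 24 hours of notification; it does not promise to go looking. Section 13.2 tells subjects to report at once, without limiting this to visits, and Section 13.3.2 has known serious events followed until resolved or explained. For a post-market study of an approved filler, relying on these routes for a month is a legitimate choice. All of this stands. A reader might infer that the protocol contradicts itself or cannot meet its own duty, and the documents do not support that.

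A reader might also conclude that each subject is checked only once after the last injection. That overlooks the same-day check at Visit 2 and the report listed after any touch-up at Visit 3. The count of one holds only for queries on a later day.

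A third objection concerns when the month starts. Section 13.3.2 does not define completion of study, and Section 10.1.1 uses nearly the same phrase for the study as a whole. It is tempting to treat starting the month at each subject's last visit as a harmless clarification. It is not: on the study-level reading it would shorten the period of mandatory reporting for subjects who finish early. This objection stands in full. On that reading the percentages above also do not apply, the time without a query is longer, and one contact at 30 days would cover only part of the window.

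Finally, consent pages are not in the copy reviewed, so what subjects are told about the extra month cannot be judged.

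**Conclusion.** The scheduling fact is certain: no adverse event query is planned after a subject's last visit, so capture in the added month is passive only. On the assumption of 30 days from the last visit, the time without a query is about 68% (64–73%) of the period since first injection without a touch-up. With a touch-up it is 52% (49–55%, or 47–58% if both visit windows add up).

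These figures might be read as the proportion of events that would be missed. They are not: the documents give neither a late-event rate nor a capture rate, and passive routes remain open throughout. The gain from an active query is therefore unknown and could be small.

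This is a low-cost improvement to consider, not the correction of an error. It leaves endpoints, sample size and inference unchanged.

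**What to change.** Add to Section 9 and Appendix A one recorded telephone or e-mail adverse event query about 30 days after each subject's last visit (Visit 3 without a touch-up, Visit 4 with one). Record non-response as well, so that an unanswered contact is not read as no event.

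Leave the window in Section 13.3.2 as written; in particular, do not restate it as running from the subject's last visit.

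Cost: about 20 short contacts by existing staff, with no extra visit or procedure; a case report form entry; and an amendment that Section 14.1 requires both the sponsor and the IRB to approve, possibly with revised consent wording.

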## **14 QUALITY ASSURANCE**

### **14.1 Institutional Review Board Approval**

An IRB shall review and have authority to approve, require modifications, or disapprove the investigation. Accordingly, this protocol, the informed consent document, and any relevant supporting information must be submitted to the IRB for review and receive approval prior to study initiation. Except in an emergency, any amendments to the protocol require approval by both Sponsor and the IRB prior to their implementation.

Additionally, the PI is responsible for providing the IRB with progress reports of the investigation at regular intervals (at least once per year) as well as with any other accurate, complete, and current information that the IRB may request concerning the investigation.

### **14.2 Informed Consent**

Informed consent shall be documented by the use of a written consent form approved by the IRB and signed by the subject or the subject's legally authorized representative. A copy of the final, IRB-approved document must be provided for record-keeping purposes. Originals of the IRB-approved consent form and sign individual consent documents must be retained in the site's study files. Each subject must be provided with a copy of his/her signed consent form.

### **14.3 Study Monitoring**

The PI will allow designees from the study sponsor to periodically audit all CRFs and corresponding source documents for each subjects, as well as, any data related to the study file. The monitoring visits provide for an opportunity to evaluate the progress of the study, to verify the accuracy and completeness of CRFs, to resolve any inconsistencies in the study records, and to assure that all protocol requirements, applicable regulations, and Investigator's obligations are being met. The PI must maintain source documents such as lab reports, photographs, history, and physical examination reports, etc., for possible review.

#### **14.4 Modification of Protocol**

If modification of the protocol is necessary, the modification must be confirmed with the IRB. No changes to the protocol that would significantly affect the safety, scope, or quality of the study may be implemented prior to written approval of the IRB. Changes to the protocol, however, may be made when necessary for the health of the subject. All modifications must be documented at the site. Moreover, if the study protocol is revised at any point during the study, IRB will be notified according to CRF 21 Part 812.

#### **14.5 Departure from the Protocol**

Minor deviations to the study protocol may be permitted if they will not increase the subject's risk or affect the validity of the study. All deviations must be documented at the study site.

When an emergency occurs that requires a departure from the protocol for an individual, a departure will be only for that subject. The PI in such an emergency will, if circumstances and time permit, contact the IRB prior to departing from the protocol. If this is not possible, such contact must be made as soon as possible in order to allow for an evaluation of the significance of such departure to the affected subject and to other subjects and to permit a decision as to whether or not the subject, for whom the departure from the protocol was affected, is to continue in the study. The CRFs will completely describe the departure from the protocol and state the reasons for such departure. In addition, IRB will be notified in writing of such departure from protocol.

#### **14.6 Confidentiality of Subject Records**

The information obtained during the conduct of this study is confidential, and will be disclosed only to the Investigator and regulatory authorities as deemed necessary and/or as required by law. The PI must provide full disclosure of all study data and make study files available for inspection upon request by the IRB and/or relevant authorities including the study sponsor. Upon notice, the local authorities may inspect and copy records that identify subjects through number and initial combinations. However, such copies have to be blinded (i.e., all personally identifiable data have to be blacked out) in order to prevent identification. The sponsor will be notified of any impending inspections relating to the study.

#### **14.7 Record Retention**

The PI shall maintain accurate, complete, and current records relating to the participation in this study, including the following:

1. All correspondence including required reports
2. Records of device shipment and disposition
3. Signed Investigator Agreements
4. The protocol and any protocol amendments
5. Records concerning adverse events whether anticipated or not
6. Documentation of each subject's case history and exposure to the device, including any CRFs, signed and dated consent forms, and any relevant medical records

7. Any other records that the applicable authorities require to be maintained by regulation or by specific requirement for a particular device or category of devices

The PI shall maintain all detailed essential documents for the duration of the investigation and for a period of at least 2 years since the formal discontinuation of clinical development of the investigational product, or 2 years after the last approval of any marketing application, or as required by the applicable regulatory requirements, whichever is a longer period.

#### **14.8 Additional Principal Investigator Responsibilities**

The PI is responsible for protecting the rights, safety, and welfare of subjects under his/her care. The PI is responsible for ensuring that the study is conducted according to the signed agreement with the investigational protocol, applicable regulations, and any condition of approval imposed by the IRB.

## 15 APPENDICES

### Appendix A Schedule of Events

Study Visit	Visit 1: Screening	Visit 2: Treatment	Visit 3: OCR Evaluation	Visit 4: 14-Day Post-OCR	Post-Visit Evaluation
Scheduled Assessment Day	≤ -14	1	14 (±3)	28 (±3)	
Informed Consent	X				
Confirm Enrollment Criteria	X				
Demographics	X				
Photo- and Videography	X		X c	X d	
Safety Evaluations					
Medical History	X				
Vital Signs	X				
Urine Pregnancy Test a	X	X b			
Adverse Events		X	X	X	
Concomitant Medications	X	X	X	X	
Patient-Reported Outcomes					
SHS	X		X c	X d	
MH	X		X c	X d	
S-GAIS			X c	X d	
PI-Reported Outcomes					
OCSS		X	X c	X d	
POLSS		X	X c	X d	
OCR Evaluation			X		
PI-GAIS			X c	X d	
Blinded Evaluator-Reported Outcomes					
FIQ					X

a For females of child-bearing age

b If the period between Visit 1, Screening Assessments and Visit 2, Treatment is greater than 14 days

c Subjects who have achieved OCR

d Subjects who required a touch-up injection in Visit 3

## Appendix C The Happiness Measures (HM)

DATE \_\_\_\_\_

NAME \_\_\_\_\_

AGE \_\_\_\_\_ SEX \_\_\_\_\_

### EMOTIONS QUESTIONNAIRE

**PART I:** Use the list below to answer the following question: IN GENERAL, HOW HAPPY OR UNHAPPY DO YOU USUALLY FEEL? Check the one statement below that best describes your *average happiness*.

Check just one of these

- 10. Extremely happy (feeling ecstatic, joyous, fantastic!)
- 9. Very happy (feeling really good, elated!)
- 8. Pretty happy (spirits high, feeling good.)
- 7. Mildly happy (feeling fairly good and somewhat cheerful.)
- 6. Slightly happy (just a bit above neutral.)
- 5. Neutral (not particularly happy or unhappy.)
- 4. Slightly unhappy (just a bit below neutral.)
- 3. Mildly unhappy (just a little low.)
- 2. Pretty unhappy (somewhat "blue", spirits down.)
- 1. Very unhappy (depressed, spirits very low.)
- 0. Extremely unhappy (utterly depressed, completely down.)

**PART II:** Consider your emotions a moment further. *On the average*, what percent of the time do you feel happy? What percent of the time do you feel unhappy? What percent of the time do you feel neutral (neither happy nor unhappy)? Write down your best estimates, as well as you can, in the spaces below. Make sure the three figures add-up to 100%.

ON THE AVERAGE:

The percent of time I feel happy \_\_\_\_\_

% The percent of time I feel unhappy \_\_\_\_\_%

The percent of time I feel neutral \_\_\_\_\_

---

\_\_\_\_\_ %  
TOTAL — 100 — %

## Appendix D Subject Global Aesthetic Improvement Scale (S-GAIS)

Please rate the change in your appearance now as compared to before you received the Restylane® Silk lip rejuvenation treatment. Please circle the appropriate number that **you believe** corresponds to the change in your appearance.

Rating	Description	
1	Very Much Improved	Optimal cosmetic result in subject
2	Much Improved	Marked improvement in appearance from the initial condition but not completely optimal for this subject
3	Improved	Obvious improvement in appearance from initial condition but a re-treatment is indicated
4	No Change	The appearance is essentially the same as the original condition
5	Worse	The appearance is worse than the original condition

## Appendix E PI Global Aesthetic Improvement Scale (PI-GAIS)

Please rate the change in the patient's appearance now as compared to before the Restylane® Silk lip rejuvenation treatment. Please circle the appropriate number that you believe corresponds to the change in the subject's appearance.

Rating	Description	
1	Very Much Improved	Optimal cosmetic result in subject
2	Much Improved	Marked improvement in appearance from the initial condition but not completely optimal for this subject
3	Improved	Obvious improvement in appearance from initial condition but a re-treatment is indicated
4	No Change	The appearance is essentially the same as the original condition
5	Worse	The appearance is worse than the original condition

